3.2 ETOPOSIDE

- **Common Tradenames (See Complete Tradename Listing)**
 - VEPESID
- **Class**
 - antineoplastic
 - mitotic inhibitor
- **Dosage, Adult (usual)**
 - Lung cancer, small cell: Range, 35 mg/m²/day IV for 4 days, to 50 mg/m²/day IV for 5 days; in combination with other approved chemotherapeutic agents; repeat at 3-4 week intervals
 - Lung cancer, small cell: ORAL dose is 2 times the IV dose rounded to the nearest 50 mg (VePesid[®])
 - Bone marrow transplantation: 2 g/m² IV over 24 hrs followed by filgrastim has been used for peripheral blood progenitor cell mobilization
 - Testicular cancer: range, 50-100 mg/m²/day IV, days 1-5 to 100 mg/m²/day IV on days 1,3, and 5; in combination with other approved chemotherapeutic agents; repeat at 3-4 week intervals
- **Administration**
 - administer over 30-60 min to avoid hypotension; avoid skin contact; do not use acrylic or ABS plastic devices with undiluted VePesid[®] for injection
 - store in the refrigerator
 - dilute with D5W or NS to conc of 0.2-0.4 mg/mL, stability 24 hrs; MAXIMUM concentration 0.4 mg/mL
- **Monitoring**
 - platelet count, hemoglobin, WBC count, and differential at start of therapy and prior to each subsequent cycle
 - monitor liver function tests
- **How Supplied**
 - 50 MG CAPSULE
 - 20 MG/ML SOLUTION FOR INJECTION

3.3 MESNA

- **Common Tradenames (See Complete Tradename Listing)**
 - Mesnex
- **Class**
 - Antineoplastic Agent
- **Dosage, Adult (usual)**
 - Cyclophosphamide adverse reaction, High dose; Prophylaxis - Hemorrhagic cystitis; Prophylaxis: 40% IV (W/W) of cyclophosphamide dose at 0,3,6,9 hr and IV fluids
 - Cyclophosphamide adverse reaction, Low dose; Prophylaxis - Hemorrhagic cystitis; Prophylaxis: 20 mg/kg ORALLY every 3-4 hr
 - Hemorrhagic cystitis; Prophylaxis - Ifosfamide adverse reaction; Prophylaxis: bolus IV regimen, IV bolus 20% of ifosfamide dose (w/w) at 0, 4, 8 hr
 - Hemorrhagic cystitis; Prophylaxis - Ifosfamide adverse reaction; Prophylaxis: oral tablet regimen, IV bolus 20% of ifosfamide dose (w/w) at time of infusion, tablets 40% of ifosfamide dose at 2, 6 hr
 - Hemorrhagic cystitis; Prophylaxis - Ifosfamide adverse reaction; Prophylaxis: continuous IV regimen (non-FDA approved regimen), bolus dose (20% total ifosfamide dose), then 40% of ifosfamide CIV
- **Dosage, Pediatric (usual)**
 - safety and efficacy of mesna tablets have no been established in children
 - Hemorrhagic cystitis; Prophylaxis - Ifosfamide adverse reaction; Prophylaxis: IV bolus 20% of ifosfamide dose (w/w) at 0, 4, 8 hr
- **Administration**
 - total daily dose mesna: IV regimen 60%; IV:ORAL regimen 100%
 - due to the benzyl alcohol content, the MULTIDOSE vial should not be used in neonates or infants and should be used with caution in older pediatric patients
 - IV mesna should continue 12-24 hr after the completion of ifosfamide
 - SC route has been used
 - patients who vomit within 2 hr of taking oral mesna should repeat the dose or receive IV mesna
- **Monitoring**
 - monitor nausea, vomiting, and diarrhea (occur with higher doses (80 mg/kg))
- **How Supplied**
 - Intravenous Solution: 100 MG/ML
 - Oral Tablet: 400 MG

3.4 IFOSFAMIDE

- **Common Tradenames (See Complete Tradename Listing)**
 - Ifex
- **Class**
 - Alkylating Agent
 - Antineoplastic Agent
 - Nitrogen Mustard
- **Dosage, Adult (usual)**
 - Germ cell tumor, Third-line (in combination with other antineoplastic agents) - Primary malignant neoplasm of testis, Third-line (in combination with other antineoplastic agents): 1.2 g/m² IV daily for 5 days repeated every 3 weeks; use with a prophylactic agent for hemorrhagic cystitis
 - Head and neck cancer: see specific protocols for dosage
 - Non-Hodgkin's lymphoma: see specific protocols for dosage

- Sarcoma: see specific protocols for dosage
- **Administration**
 - administer hydration (minimum 2 L/day) plus mesna to limit urotoxicity; recommended IV mesna dosing is 20% ifosfamide dosage (w/w) at the time of the ifosfamide infusion, 4 and 8 hrs after every ifosfamide dose
 - reconstitute with SWFI/BWFI to a concentration of 50 mg/ml; dilute further to 0.6-20 mg/mL in D5W, NS, LR, SWFI
 - IV infusion over at least 30 minutes
- **Monitoring**
 - monitor serum/urine chemistries including phosphorous, alkaline phosphatase, and other appropriate laboratory studies
 - complete blood counts prior to each administration; hold further therapy if white cell count is less than 2,000 or platelets less than 50,000
 - urinalysis is recommended prior to each dose; withhold doses until recovery if hematuria greater than 10 red cells per high power field is found
- **How Supplied**
 - Intravenous Powder for Solution: 1 GM, 3 GM

3.5 CARBOPLATIN

- **Common Tradenames (See Complete Tradename Listing)**
 - Paraplatin
 - Paraplatin NovaPlus
- **Class**
 - Antineoplastic Agent
 - Platinum Coordination Complex
 -
- **Administration**
 - do NOT use with infusion sets/needles containing aluminum
 - alternative dosing regimen: Calvert formula recommendations- dose(mg)= target (AUC) x (GFR + 25); area under the curve (AUC), glomerular filtration rate (GFR)
 -
- **Monitoring**
 - complete blood counts (CBC) should be taken before each course of treatment; the white blood cell count and the platelet count should be greater than or equal to 4000/mm³ and 100,000/mm³, respectively, before retreatment; routine CBCs should be checked once or twice between each course of carboplatin administration-doses should be reduced if severe myelosuppression occurs
 - renal function should be monitored, especially in patients with preexisting renal dysfunction or prior aminoglycoside therapy; baseline values of blood urea nitrogen (BUN), serum creatinine, and creatinine clearance should be established; BUN and serum creatinine should be remeasured before each course of carboplatin
 - serum electrolyte levels (sodium, calcium, magnesium, and potassium) should be measured at baseline, between courses of therapy weekly, and immediately before subsequent courses; decreases in these serum electrolytes are usually mild and reversible
 - patients who have received prior therapy with cisplatin or have had previous hearing loss should have baseline audiometry testing before receiving carboplatin; repeat testing should be performed if hearing loss is noted
 - liver function tests should be evaluated at baseline and before each course of carboplatin
 -

- **How Supplied**

- Intravenous Powder for Solution: 50 MG, 150 MG, 450 MG
- Intravenous Solution: 10 MG/ML

4.1 PATIENTS ELIGIBILITY

4.2 Inclusion Criteria

1. Histologically confirmed classical Hodgkin lymphoma (nodular sclerosis, mixed cellularity, or lymphocyte-rich classical HL).
2. Patients must have failed (relapsed or refractory) front-line standard anthracycline-containing regimen, such as ABVD, Stanford V, or BEACOPP.
3. Bidimensionally measurable disease with at least 1 lesion ≥ 2.0 cm in a single dimension
4. Acceptable hematologic status:
 - Hemoglobin ≥ 9.0 g/dL
 - Absolute neutrophil count ≥ 1500 cells/mm³
 - Platelet count $\geq 100,000$ cells/mm³
5. Normal serum K⁺, Mg⁺, PO₄, and total Ca⁺⁺ (pre-treatment abnormal values may be therapeutically corrected before starting therapy and must be documented as normal or if abnormal values persist must be documented as clinically insignificant). Albumin should be ≥ 3
6. Pre-study WHO performance status of 0, 1, or 2
7. Age ≥ 16 years
8. Voluntary signed IRB approved consent informed before performance of any study-related procedure not part of normal medical care, with the understanding that consent may be withdrawn by the subject at any time without prejudice to future medical care.
9. Patients of reproductive potential (female of child bearing potential has not been postmenopausal for at least 12 consecutive months or not surgically sterile; male of child bearing potential has not been surgically sterile) must follow accepted birth control methods (e.g. barrier method) during treatment.
10. Clinically euthyroid. Note: Patients are permitted to receive thyroid hormone supplements to treat underlying hypothyroidism.
11. Baseline MUGA or ECHO must demonstrate LVEF $\geq 50\%$.

4.3 Exclusion Criteria

1. Lymphocyte predominant histology
2. More than one prior chemotherapy regimens.
3. Prior therapy with other HDAC inhibitors, including valproic acid
4. Prior therapy with heat shock protein (HSP)-90 inhibitors
5. Prior stem cell transplant
6. Abnormal liver function:
 - Bilirubin > 2.0 mg/dL (26 μ mol/L)
 - Alkaline phosphatase > 2 x upper limits of normal (ULN)
 - AST (SGOT) and/or ALT > 2 x ULN
7. Serum creatinine > 1.5 mg/dl
8. Presence of CNS involvement with Hodgkin lymphoma
9. Presence of HIV infection or AIDS.

10. Another primary malignancy (other than squamous cell and basal cell carcinoma of the skin, in situ carcinoma of the cervix, or treated prostate cancer with a stable PSA) for which the patient has not been disease-free for at least 3 years.
11. Serious nonmalignant disease (e.g., congestive heart failure, hydronephrosis); active uncontrolled bacterial, viral, or fungal infections; or other conditions which would compromise protocol objectives in the opinion of the investigator.
12. Impaired cardiac function or clinically significant cardiac diseases, including any one of the following:
 - History or presence of sustained ventricular tachyarrhythmia.
 - Any history of ventricular fibrillation or torsade de pointes
 - Bradycardia defined as HR < 50 bpm. Patients with pacemakers are eligible if HR ≥ 50 bpm.
 - Screening ECG with a QTc > 450 msec
 - Right bundle branch block + left anterior hemiblock (bifascicular block)
 - Patients with myocardial infarction or unstable angina ≤ 6 months prior to starting study drug
 - Other clinically significant heart disease (e.g., CHF NY Heart Association class III or IV , uncontrolled hypertension, history of labile hypertension, or history of poor compliance with an antihypertensive regimen)
13. Female subject is pregnant or breast-feeding. Confirmation that the subject is not pregnant must be established by a negative serum β-human chorionic gonadotropin (β-hCG) pregnancy test result obtained during screening, unless the female has recently (within 8 weeks) undergone egg harvest, which would result in the (β-hCG) test to be elevated without pregnancy. Pregnancy testing is not required for post-menopausal or surgically sterilized women.
14. Patient has received other investigational drugs within 14 days before enrollment or who have not recovered from side effects of those therapies.
15. Serious medical or psychiatric illness likely to interfere with participation in this clinical study.
16. Impairment of GI function or GI disease that may significantly alter the absorption of panobinostat
17. Patients with diarrhea > CTCAE V.4 grade 2
18. Patients using medications that have a relative risk of prolonging the QT interval or inducing torsade de pointes if treatment cannot be discontinued or switched to a different medication prior to starting study drug
19. Patients who have received either immunotherapy within ≤ 8 weeks; chemotherapy within ≤ 3 weeks; or radiation therapy to > 30% of marrow-bearing bone within ≤ 2 weeks prior to starting study treatment; or who have not yet recovered from side effects of such therapies.
20. Patients who have undergone major surgery ≤ 4 weeks prior to starting study drug or who have not recovered from side effects of such therapy

5.1 TREATMENT PLAN

5.2 Phase-I

- 5.2.1 This is an open-label, non-randomized single-arm, Phase I, dose escalation trial to define the safety profile, the maximum tolerated dose (MTD), and the antitumor activity of panobinostat plus ICE chemotherapy administered orally in patients with relapsed/refractory classical Hodgkin lymphoma (HL).
- 5.2.2 Study assessments will include monitoring of all toxicities and adverse events, and objective tumor measurements. The National Cancer Institute (NCI) Common Terminology Criteria for Adverse Events (CTCAE), version 4.0 will be used for grading adverse events and all toxicities.

The phase-I portion of this study will conclude once the MTD has been reached, and the toxicity profile has been defined. The phase-II doses will be based on data obtained from this phase-I portion of the study.

5.1.3 Phase-I dose levels

Panobinostat + ICE combination therapy will be administered at the dose level assigned to each cohort, as outlined in Table 5. Each ICE cycle is considered to be 14 days (2 weeks). A tumor response assessment will be done within 7-13 days of completion of 3 cycles of ICE using the Revised Response Criteria for Malignant Lymphoma. Patients with a complete response (CR) or partial response (PR) will be considered for stem cell transplantation, otherwise they will be removed from the study.

Table-5: Study design for the phase-I		
Dose Level	ICE chemotherapy Day 1 and repeat every 14-days	PANOBINOSTAT (mg, orally) 3 times per week
-1	See Table 5.2	10
0	See Table 5.2	20
1	See Table 5.2	30

5.1.4 Panobinostat is given only during cycles 1 and 2 of ICE according to Table 5.1. Cycle 3 of ICE will be given without panobinostat.

5.1.5 Investigational therapy: Panobinostat (LBH589).

Panobinostat will be provided by Novartis. Oral Panobinostat will be supplied as 5-mg or 20-mg hard gelatin capsules.

Medication labels will comply with US legal requirements and be printed in English. They will supply no information about the patient. The storage conditions for study drug will be described on the medication label.

During the study, Panobinostat will be self-administered (by the patients themselves) orally three times per week.

For cycle 1 of ICE: Panobinostat will be administered starting day -6 and ICE on day 1 as outlined in Table 5.1:

Patients should be instructed to take their oral dose of Panobinostat around the same time each day. Each dose of Panobinostat should be taken with an 8 oz / 240 ml glass of water. Patients should be instructed to swallow the capsules whole and not chew them. Patients must avoid grapefruit or grapefruit juice and seville (sour) oranges during the entire study.

If the patient forgets to take his/her dose on a scheduled treatment day, then he/she should take Panobinostat on that same day within 12 hours after the missed dose if possible. After more than 12 hours, that day's dose should be withheld, and the patient should wait to take Panobinostat until the next scheduled treatment day (i.e., patients should be instructed not to try to make-up the missed dose after 12 hours). The patient should then continue treatment with the original dosing schedule. A pill diary will be provided to the subject for documentation of dosing for each cycle.

The investigator should instruct the patient to take the study drug exactly as prescribed (promote compliance). All dosages prescribed and dispensed to the patient and all dose changes during the study should be recorded. All used and unused study drug will be returned to the study site personnel.

5.1.6 Dose escalation

Standard doses of ICE chemotherapy will be used and fixed, while panobinostat doses will be escalated (Tables 5, 5.1, and 5.2). Initially, 3 patients will be treated at each dose level and will be monitored for dose limiting toxicities (DLT) for 14 days from the first dose of ICE. If no DLTs are observed in those 3 patients at the end of the observation period, escalation to the next dose level may commence. If a DLT is observed in 1 of the first 3 patients, the cohort will be expanded to a maximum of 6 patients. If 2 or more DLTs are observed in any cohort, no further escalation will take place. The maximum tolerated dose (MTD) will have been exceeded, and the preceding dose level will be recommended for the Phase-II portion of this study. If DLTs are observed in 0 dose level, -1 dose level will be evaluated for DLTs before recommending it as MTD.

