5.1.13 Maximum Tolerated Dose (MTD)

The MTD will be the highest dose at which no more than 1 in 6 of the patients in the cohort experiences one or more DLTs in the first treatment cycle (21 days from the first dose of panobinostat and 14 days from the first dose of ICE).

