9.2 Termination of Treatment and/or Study Participation

Patients will be informed that they have the right to withdraw from the study at any time for any reason, without prejudice to their medical care. The investigator also has the right to withdraw patients from the study for any of the following reasons:

- Intercurrent illness
- Occurrence of an unacceptable adverse event
- A treatment cycle delay of ICE > 14 days
- Patient request
- Protocol violations
- Non-compliance
- Administrative reasons
- Failure to return for follow-up
- General or specific changes in the patient's condition unacceptable for further treatment in the judgment of the investigator
- Progressive disease.

At the time of withdrawal, all study procedures outlined for the End of Study visit should be completed. The primary reason for a patient's withdrawal from the study is to be recorded in the source documents.

All AEs will be followed for 30 days post last dose of study drug and recorded in database

10.0 STATISTICAL CONSIDERATION:

Phase I design:

The objective of the phase I portion is to determine the maximum tolerated dose (MTD) of Panobinostat in combination with ICE. The dose level for ICE is fixed. There are three predefined dose levels for Panobinostat.

Dose Level	Panobinostat (mg, orally) Monday-Wednesday-Friday
-1	10
0	20
1	30

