The standard “3+3” design will be used for the phase I portion of the trial. Dose limiting toxicity (DLT) is defined as follows: for non-hematologic toxicities, any CTCAE v4.0 Grade 3 or greater toxicity except for grade 3 fatigue, grade 3 or 4 nausea and vomiting lasting less than 72 hours after the last dose of chemotherapy, and grade 3 non-hematologic laboratory abnormalities that resolve to grade 1 or baseline (if the patient entered the study with existing toxicity) within 14 days of the first dose of ICE chemotherapy; for hematologic toxicities using CTCAE v4.0, grade 4 neutropenia lasting greater than 14 days, grade 3 febrile neutropenia requiring antibiotics, grade 4 febrile neutropenia, and Grade 4 platelet count ($<25,000/\text{mm}^3$) at any time and lasting greater than 14 days. Applying the 3+3 design, the first cohort of 3 patients will be treated at dose level 0 and evaluated for DLT at the end of first cycle. The algorithm is as follows: (1) If 0 out of 3 patients experiences dose-limiting toxicity (DLT), the next cohort of 3 patients will be treated at the next higher dose level. (2) If 1 out of 3 patients develop a DLT, an additional 3 patients will be treated at the same dose level. If no more DLTs develop at this dose, i.e. 1 out of a total of 6 patients develops a DLT, the dose escalation continues for the next cohort of 3 patients. (3) At any given dose, if greater than 1 out of 3 patients or 1 out of 6 patients experience DLT, the dose level exceeds the MTD and 3 more patients will be treated at the next lower dose if there are less than 6 patients already treated at that dose. Following the above scheme, MTD is defined as the highest dose level in which 6 patients have been treated with less than 2 instances of DLT. Given 3 predefined dose levels, it is anticipated that up to 12 eligible patients are required for the dose-finding portion of this trial.

To better estimate the DLT rate, an expansion cohort of 10 patients will be treated at the MTD. If at any time the DLT rate exceeds 33%, then the MTD is too toxic and a lower dose than MTD will be selected for the phase II.

With the addition of Dosing Schedule B, an additional 10 patients will be treated at the MTD in a 2nd expansion cohort but at a different dosing schedule to better evaluate safety and administration of ICE.

Phase II:

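### Sections 5.1.6, 5.1.13 and 10.0 give conflicting rules for the MTD, and the anticipated 12 dose-finding patients is not the maximum of section 10.0's own algorithm

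*Combined protocol and SAP*

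**What the plan says.** Three places govern the choice of the MTD.

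- **Section 5.1.6 (Dose escalation).** Three patients are treated per level. "If no DLTs are observed in those 3 patients at the end of the observation period, escalation to the next dose level may commence". One patient with a DLT among the first three leads to expansion to at most six. "If 2 or more DLTs are observed in any cohort, no further escalation will take place", and then: "The maximum tolerated dose (MTD) will have been exceeded, and the preceding dose level will be recommended for the Phase-II portion of this study". Only level -1 is expressly to be evaluated before it is recommended.
- **Section 5.1.13 (MTD).** The MTD is the "highest dose at which no more than 1 in 6 of the patients in the cohort experiences one or more DLTs".
- **Section 10.0 (Statistical Consideration, Phase I design).** "There are three predefined dose levels for Panobinostat", and "the first cohort of 3 patients will be treated at dose level 0". Once a level is exceeded, three more patients go to the next lower level if fewer than six have been treated there. The definition is: "MTD is defined as the highest dose level in which 6 patients have been treated with less than 2 instances of DLT". On size: "it is anticipated that up to 12 eligible patients are required for the dose-finding portion of this trial".

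Section 10.0 then adds a ten-patient expansion at the MTD, with a lower dose chosen for phase II if the DLT rate exceeds 33%. Its Phase II part takes the dose determined after that expansion.

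**The concern.** Read literally, the three sections differ in two ways that bear on the dose, and the stated size agrees with only one of them.

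1. **Evidence at the recommended level.** A level left after 0/3 and returned to because the next level failed is recommended as it stands in 5.1.6. In 10.0 it must first be filled to six patients and pass.
2. **Counting unit.** The stopping clause in 5.1.6 and the MTD definition in 10.0 count DLTs. Section 5.1.13 and the algorithm steps in 10.0 count patients.
3. **Size.** The anticipated maximum of 12 fits 5.1.6, but it stands in 10.0, whose algorithm can use more.

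At stake is whether the MTD follows from one rule that can be reproduced. It fixes the dose for both expansion cohorts and for the randomised panobinostat arm.

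**Working it through.** **Inputs.** From the documents: three levels (-1, 0, 1), start at level 0, cohorts of three, and the rules above. True DLT rates are not given, so every rate below is an assumption. The rates affect the probabilities but not the maximum sizes. In the probability calculations each patient with a DLT has one DLT.

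**Step 1: reproduce the 12.** Under 5.1.6 the trial never returns to a level already left, so at most two levels are used: 0 and 1, or 0 and -1. The maximum is 6 + 6 = 12, which matches the stated figure.

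**Step 2: maximum under 10.0.** Take level 0 with 0/3; level 1 with 1/3, expanded to six and failing with at least 2/6; three more at level 0, at least two of them with a DLT; then level -1 with 1/3, expanded to six. The total is 6 (level 0) + 6 (level 1) + 6 (level -1) = 18. Each move on this path is an explicit step of 10.0. The possible totals are 6, 9, 12, 15 and 18.

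**Step 3: how often 12 is exceeded under 10.0.** This needs 0/3 at level 0, failure of level 1, and then at least 2 of 3 on return to level 0:

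P(N>12) = P(0/3 at level 0) x P(at least 2/3 at level 0) x [P(level 1 fails on six) + P(level 1 fails on three) x P(level -1 is filled to six)]

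With assumed rates 0.20/0.30/0.50 for levels -1/0/1:
- Level 0: 0.343 x 0.216 = 0.0741.
- Level 1 fails on three: 0.500. Level 1 fails on six: 0.125 x 0.500 + 0.375 x 0.875 = 0.391.
- Level -1 has at most 1/3 and is filled to six: 0.896.
- P(N>12) = 0.0741 x (0.391 + 0.500 x 0.896) = 0.062.

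The same formula gives 0.007 at 0.05/0.10/0.20 and 0.068 at 0.20/0.40/0.60, so about 1-7%.

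**Step 4: three versus six patients.** After 0/3 at level 0 and failure of level 1, 10.0 rejects level 0 if at least two of the three added patients have a DLT: 3p²(1-p) + p³.

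| Assumed DLT rate at level 0 | Level 0 overturned under 10.0 |
|---|---|
| 10% | 0.028 |
| 20% | 0.104 |
| 30% | 0.216 |
| 40% | 0.352 |

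Section 5.1.6 has no such step. Over eight assumed rate sets (seven rising from 0.05/0.10/0.20 to 0.20/0.30/0.50, and a flat 0.33), it recommends level 0 on only three patients in 17% to 35% of trials; 10.0 never does.

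**Step 5: effect on the MTD.** With the steep set 0.20/0.40/0.60:
- 5.1.6 recommends level 0 or 1 with probability 0.216 + 0.432 x 0.216 = 0.309.
- 10.0 removes the cases overturned on return: 0.309 - 0.216 x 0.959 x 0.352 = 0.236, where 0.959 is the chance that level 1 fails.

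**Step 6: effect after the expansion.** Four of ten is the smallest count above 33%. With one look at ten patients, P(at least 4/10) is 0.12, 0.35 or 0.62 at true rates of 20%, 30% or 40%. For the rates of Step 5, the chance that level 0 or 1 is the MTD and also passes the expansion is 11.0% under 5.1.6 and 8.6% under 10.0 (ignoring a fall from level 1 to level 0).

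**Step 7: counting unit, with no assumed rates.** Suppose one patient of six has two separate DLTs and the other five have none.

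| Wording | Count | Result |
|---|---|---|
| 5.1.13 | 1 patient of 6 | acceptable |
| 10.0, algorithm steps | 1 patient of 6 | acceptable |
| 5.1.6, stopping clause | 2 DLTs | stop; level exceeded |
| 10.0, MTD definition | 2 instances | not the MTD |

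Identical data give different answers, including within 10.0.

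**The case against.** The best defence has four parts.

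- **A later safeguard exists.** Every MTD goes through ten more patients and the 33% check before phase II. This stands. At 20%, 30% and 40% the expansion rejects a level more often (0.12, 0.35, 0.62) than 10.0's three-patient return cohort does (0.10, 0.22, 0.35).
- **Escalation looks finished.** Section 2.5 reports 21 patients enrolled and section 5.1.7 reports ten in the schedule A expansion. If those ten are among the 21, 21 - 10 = 11 were in dose finding, within 12. This also stands as an inference. It makes the issue largely one of documenting the MTD, although section 2.5 leaves room for additional cohorts.
- **5.1.6 is an abbreviated summary.** It does not say that three patients suffice, and its expansion clause counts patients. Read with 10.0, six patients and a patient count may be what was meant. That is plausible, but 5.1.13 can be read as a proportion or as a six-patient requirement, and 10.0 itself mixes the two units. The text does not settle it.
- **The 12 is only anticipated.** This is fair: it is not written as a cap and would seldom be exceeded.

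A reader might also infer that the fallback after a failed expansion breaks a six-patient rule, because the lower level may have had only three patients. No section requires six patients there, so this is not a contradiction.

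**Conclusion.** The rules conflict as written and should be reconciled. The counting conflict rests on the text alone, as do the maxima of 18 under 10.0 and 12 under 5.1.6. The chance of overturning level 0 (0.10 to 0.35 for true rates of 20% to 40%) and of exceeding 12 patients (about 1-7%) depends on assumed DLT rates.

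A reader might infer that the wrong dose is going into phase II, or that the two rules put the phase II dose about 7 points apart (0.309 versus 0.236). The documents do not support either. The 7-point gap is the MTD before expansion, under a steep assumed rate set; after the expansion check the same rates leave about 2 points (11.0% versus 8.6%). Nor do the documents show which rule was applied, or that the MTD in use would differ under the other.

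**What to change.** - Reconcile 5.1.6, 5.1.13 and 10.0 into one rule, chosen by the sponsor, that says whether a level returned to must be filled to six patients before it is recommended.
- Use one counting unit throughout, either patients with at least one DLT or DLT events.
- State which rule produced the MTD now in use, with the number of patients and DLTs at each level.
- Restate the dose-finding size to match: maximum 18 if the rule is that of 10.0, or 12 if it is that of 5.1.6. An expected number may be given beside the maximum.

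No dose or dose-selection rule is proposed here. The cost is wording in three sections and a short record of the escalation already done. Any extra patients in a further cohort would be those the chosen rule already requires.
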